## RESEARCH SITES

0 unresolved  
comment(s)

To complete this section, ensure the responses are accurate then click "SAVE".

A) Check all the applicable sites listed below at which the research will be conducted. If none apply, you do not need to check any boxes.

## UK Sites

- UK Classroom(s)/Lab(s)
- UK Clinics in Lexington
- UK Clinics outside of Lexington
- UK Healthcare Good Samaritan Hospital
- UK Hospital

## Schools/Education Institutions

- Fayette Co. School Systems \*
- Other State/Regional School Systems
- Institutions of Higher Education (other than UK)

\*Fayette Co. School systems, as well as other non-UK sites, have additional requirements that must be addressed. See ORI's [IRB Application Instructions - Off-site Research](#) web page for details.

## Other Medical Facilities

- Bluegrass Regional Mental Health Retardation Board
- Cardinal Hill Hospital
- Eastern State Hospital
- Norton Healthcare
- Nursing Homes
- Shriner's Children's Hospital
- Veterans Affairs Medical Center
- Other Hospitals and Med. Centers

- Correctional Facilities
- Home Health Agencies
- International Sites

Research activities conducted at performance sites that are not owned or operated by the University of Kentucky (UK) or at sites that do not fall under the UK IRB's authority, are subject to special procedures for coordination of research review. Additional information is required (see [IRB Application Instructions - Off-Site Research](#) web page), including:

- A letter of support and local context is required from non-UK sites. See *Letters of Support and Local Context* on the [IRB Application Instructions - Off-Site Research](#) web page for more information.
- Supportive documentation, including letters of support, can be attached below. When attaching reliance documents, please ensure that you select the correct 'Document Type' from the drop-down menu. See below for the "Document Types" in bold, followed by examples of reliance documents for each type:
  - **Individual Investigator Agreement (IIA)**
    - A completed Individual Investigator Agreement

- **IRB Approval (Non-UK)**
  - A Letter of Approval from a Non-UK IRB
- **IRB Authorization Agreement (IIA)**
  - A SMART IRB Agreement
  - An OHRP Agreement
  - A DoD Agreement
  - An IREX Reliance Notification
  - Any Reliance Agreement
- **Letter of Support & Local Context**
  - A Letter of Support from an organization at which some research activities are occurring
  - Communications Plan
  - Local Context Form

Please reach out to [[contact]](mailto:[contact]) if you have any questions or concerns.

- NOTE: If the non-UK sites or non-UK personnel are engaged in the research, there are additional federal and university requirements which need to be completed for their participation. For instance, the other site(s) may need to complete their own IRB review, or a cooperative review arrangement may need to be established with non-UK sites.
- Questions about the participation of non-UK sites/personnel should be discussed with the ORI staff at [contact].

List all other non-UK owned/operated locations where the research will be conducted:

The research will occur in churches and community centers located in Kentucky. Once we have identified the sites we will submit the Letters of Support/church registration forms by amendment.

Describe the role of any non-UK site(s) or non-UK personnel who will be participating in your research.

Please describe the plan for the management of reporting unanticipated problems, noncompliance, and submission of protocol modifications and interim results from the non-UK sites:

B) If your research involves collaboration with any sites and/or personnel outside the University of Kentucky, then it is considered multisite research and IRB reliance issues will need to be addressed. This may include national multi-center trials as well local studies involving sites/personnel external to UK. If you would like to request that the University of Kentucky IRB (UK IRB) serve as the lead IRB for your study, or if you would like the UK IRB to defer review to another IRB, please contact the [[contact]](mailto:[contact]).

## RESEARCH ATTRIBUTES

0 unresolved  
comment(s)

Instructions: For various reasons, it is necessary to determine whether your research activities meet the definition of clinical research and/or a clinical trial. Your responses to the next series of questions will make that determination. For more details on the definitions, go to ORI's [clinical research vs. clinical trial web page](#) or visit [NIH's decision tree](#) for the NIH Clinical Trial definition.

Contact the Clinical Research Support Office (CRSO) if your study provides clinical services (e.g., labs, biopsies, tissue samples, physical exams, PT, counseling) regardless of payer (grant, federal, UK, industry), utilizes UKHC space, or meets the NIH definition of a clinical trial (thereby requiring registry with CT.gov) as your study will need to be entered in OnCore to ensure appropriate regulatory tracking and billing. Visit [CRSO FAQs](#) for more information; requests for CCTS/CRSO services can be submitted via their [service request form](#). For other questions, you can contact the CRSO Director, [name], at [[contact]](mailto:[contact]).

My research activities include one or more of the following:

Patient-oriented research regarding mechanisms of human disease, therapeutic interventions, clinical studies, or development of new technologies

Yes  No

Material of human origin (such as tissues, specimens, and cognitive phenomena) for which an investigator (or colleague) directly interacts with human subjects

Yes  No

Epidemiologic or Behavioral Studies

Yes  No

Outcomes Research or Health Services Research

Yes  No

Indicate the items below that apply to your research. Depending on the items applicable to your research, you may be required to complete additional forms or meet additional requirements. Contact the ORI [contact]) if you have questions about additional requirements.

Not applicable

Check All That Apply

- Academic Degree/Required Research
- Alcohol/Drug/Substance Abuse Research
- Biological Specimen Bank Creation (for sharing)
- Cancer Research
- CCTS-Center for Clinical & Translational Science
- Certificate of Confidentiality
- Collection of Biological Specimens for banking and use
- Community-Based Participatory Research
- Deception
- Educational/Student Records (e.g., GPA, test scores)
- Emergency Use (Single Patient)
- Gene Transfer
- Genetic Research
- NIH Genomic Data Sharing (GDS) (databases such as GWAS, dbGaP, GenBank)
- Treatment with Human Cells, Tissues, and Cellular and Tissue Based Products
- Individual Expanded Access or Compassionate Use

For additional requirements and information:

- [Cancer Research \(MCC PRMC\)](#)
- [Certificate of Confidentiality](#) (look up "Confidentiality/Privacy...")
- [CCTS \(Center for Clinical and Translational Science\)](#)
- [Clinical Research](#) (look up "What is the definition of....")
- [Clinical Trial](#)
- [Collection of Biological Specimens for Banking](#) (look up "Banks, Repositories, Registries...")
- [Collection of Biological Specimens](#) (look up "Repositories, Registries, Specimen/Tissue Banks...")
- [Community-Based Participatory Research](#) (look up "Community-Engaged...")
- [Data & Safety Monitoring Board \(DSMB\)](#)

\*For Medical IRB: [Service Request Form](#) for CCTS DSMB

- [Data & Safety Monitoring Plan](#)
- [Deception\\*](#)

\*For deception research, also go to the E-IRB Application Informed Consent section, checkmark and complete "Request for Waiver of Informed Consent Process"

- [Emergency Use \(Single Patient\) \[attach\]](#)

- International Research
- Planned Emergency Research Involving Exception from Informed Consent
- Recombinant DNA
- Registry or data repository creation
- Stem Cell Research
- Suicide Ideation or Behavior Research
- Survey Research
- Transplants
- Use, storage and disposal of radioactive material and radiation producing devices
- Vaccine Trials

[Emergency Use Checklist](#) (PDF)

- [Genetic Research](#) (look up "Banks, Repositories, ...Genetic/Genomic Data Sharing...")
- [Gene Transfer](#)

\*For gene transfer research, also go to the E-IRB Application Other Review Committees section, and checkmark Institutional Biosafety Committee

- [International Research](#) (look up "International & Non-English Speaking")
- [NIH Genomic Data Sharing \(GDS\) Policy](#) (PDF)
- [Planned Emergency Research Involving Exception to Informed Consent\\*](#)

\*For Planned Emergency Research Involving Waiver of Informed Consent, also go to the E-IRB Application Informed Consent section, checkmark and complete "Request for Waiver of Informed Consent Process"

- [Use, storage and disposal of radioactive material and radiation producing devices](#)

## FUNDING/SUPPORT

0 unresolved  
comment(s)

If the research is being submitted to, supported by, or conducted in cooperation with an external or internal agency or funding program, indicate below all the categories that apply. [?](#)

Not applicable

## Check All That Apply

- Grant application pending
- (HHS) Dept. of Health & Human Services
- (NIH) National Institutes of Health
- (CDC) Centers for Disease Control & Prevention
- (HRSA) Health Resources and Services Administration
- (SAMHSA) Substance Abuse and Mental Health Services Administration
- (DoJ) Department of Justice or Bureau of Prisons
- (DoE) Department of Energy
- (EPA) Environmental Protection Agency
- Federal Agencies Other Than Those Listed Here
- Industry (Other than Pharmaceutical Companies)
- Internal Grant Program w/ proposal
- Internal Grant Program w/o proposal
- National Science Foundation
- Other Institutions of Higher Education
- Pharmaceutical Company
- Private Foundation/Association
- U.S. Department of Education
- State

Other:

Specify the funding source and/or cooperating organization(s) (e.g., National Cancer Institute, Ford Foundation, Eli Lilly & Company, South Western Oncology Group, Bureau of Prisons, etc.):

## Add Related Grants

If applicable, please search for and select the OSPA Account number or Electronic Internal Approval Form (eIAF) # (notif #) associated with this IRB application using the "Add Related Grants" button.  
If required by your funding agency, upload your grant using the "Grant/Contract Attachments" button.

[Add Related Grants](#)

[Grant/Contract Attachments](#)

The research involves use of Department of Defense (DoD) funding, military personnel, DoD facilities, or other DoD resources. (See [DoD SOP](#) and [DoD Summary](#) for details)

Yes  No

Using the "attachments" button (below), attach applicable materials addressing the specific processes described in the DoD SOP.

[DOD SOP Attachments](#)

Additional Certification: (If your project is federally funded, your funding agency may request an Assurance/ Certification/Declaration of Exemption form.) Check the following if needed:

Protection of Human Subjects Assurance/Certification/Declaration of Exemption (Formerly Optional Form – 310)

Assurance/Certification Attachments

## OTHER REVIEW COMMITTEES

0 unresolved  
comment(s)

If you check any of the below committees, additional materials may be required with your application submission.

Does your research fall under the purview of any of the other review committees listed below? [If yes, check all that apply and attach applicable materials using the attachment button at the bottom of your screen.]

Yes  No

Additional Information	
 Institutional Biosafety Committee  Radiation Safety Committee  Radioactive Drug Research Committee  Markey Cancer Center (MCC) Protocol Review and Monitoring Committee (PRMC)  Graduate Medical Education Committee (GME)  Office of Medical Education (OME)	
 
• Institutional Biosafety Committee (IBC) - Attach required IBC materials
 
• Radiation Safety Committee (RSC) - For applicability, see instructions
 
• Radioactive Drug Research Committee (RDRC)
 
• Markey Cancer Center (MCC) Protocol Review and Monitoring Committee (PRMC)** - Attach MCC PRMC materials, if any, per instructions.
 
• Office of Medical Education (OME)
 
• Graduate Medical Education Committee (GME)
 

	

** If your study involves cancer research, be sure to select "Cancer Research" in the "Research Attributes" section. ORI will send your research protocol to the Markey Cancer Center (MCC) Protocol Review and Monitoring Committee (PRMC). The MCC PRMC is responsible for determining whether the study meets the National Cancer Institute (NCI) definition of a clinical trial and for issuing documentation to you (the investigator) which confirms either that PRMC approval has been obtained or that PRMC review is not required. Your IRB application will be processed and reviewed independently from the PRMC review.
	

**ADDITIONAL INFORMATION/MATERIALS****0 unresolved  
comment(s)**

Do you want specific information inserted into your approval letter?  Yes  No

**Approval Letter Details:**

If you wish to have specific language included in your approval letter (e.g., serial #, internal tracking identifier, etc...), type that language in the box below exactly as it should appear in the letter. The text you enter will automatically appear at the top of all approval letters, identical to how you typed it, until you update it. Don't include instructions or questions to ORI staff as those will appear in your approval letter. **If these details need to be changed for any reason, you are responsible for updating the content of this field.**

**Additional Materials:**

If you have other materials you would like to include for the IRB's consideration, check all that apply and attach the corresponding documents using the Attachments button below.

- Detailed protocol
- Dept. of Health & Human Services (DHHS) approved protocol (such as NIH sponsored Cooperative Group Clinical Trial)
- Other Documents

**Protocol/Other Attachments**

**NOTE: [Instructions for Dept. of Health & Human Services \(DHHS\)-approved protocol](#)**

If you have password protected documents, that feature should be disabled prior to uploading to ensure access for IRB review.

To view the materials currently attached to your application, click "All Attachments" on the left menu bar.

Each Section/Subsection in the menu on the left must have a checkmark beside it (except this Submission section) indicating the Section/Subsection has been completed. Otherwise your submission for IRB review and approval cannot be sent to the Office of Research Integrity/IRB.

If applicable, remember to update the Approval Letter Details text box under the Additional Information section

If your materials require review at a convened IRB meeting which you will be asked to attend, it will be scheduled on the next available agenda and you will receive a message to notify you of the date.

If you are making a change to an attachment, you need to delete the attachment, upload a highlighted version that contains the changes (use Document Type of "Highlighted Changes"), and a version that contains the changes without any highlights (use the appropriate Document Type for the item(s)). Do **not** delete approved attachments that are still in use.

Your protocol has been submitted.

## CT Gov analysis plan

We analyzed study data descriptively, via means and standard deviations (SD) or frequency distributions, both as a summary of variables at each time point and as a check for missing and out-of-range values. We used T-tests and Chi Square tests of association to make baseline demographic comparisons between the treatment and comparison groups and between those who completed the study and those who were retained in the analytic sample but were missing one or both follow-up weights at 12 and 24 weeks. We evaluated means, SD, and Pearson product moment correlations among the variables indicating percent weight loss at 4, 12, and 24 weeks, with percentage of classes attended, and for the treatment group nonresponders the number of completed CHW calls.

We accounted for the cluster-randomized design and used repeated measures mixed modeling to evaluate the percent decrease in weight over *Time* (timepoints of 4 weeks, 12 weeks, and 24 weeks, relative to weight at baseline), between *Intervention Conditions* (Treatment vs. Comparison), and by *Response status* (responder vs. nonresponse). In addition to these main effects, we included the two- and three-way interaction terms. We included covariates that had the largest observed differences between the Treatment vs. Comparison group and/or those who completed the study versus those who missed one or both 12 and 24-week data collections. We evaluated post-hoc pairwise differences using Fisher's least significant difference procedure for pre-planned comparisons. The data analysis was done using SAS, v. 9.4; an alpha level of .05 was used for inferential testing.

For the cost effectiveness analysis we evaluated the cost of the intervention arm by comparing the incremental cost and weight loss with the active control arm (Aim 3). We compared the cost and outcomes associated with the intervention arm relative to the active control arm by calculating ICERs. An ICER is the ratio of the incremental change in costs divided by the incremental change in outcomes. Our primary cost effectiveness analysis focused on incremental cost per kilogram (kg) lost.

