Obesity is the number one and most preventable Type 2 diabetes (T2D) risk factor, yet despite a \$20 billion annual expenditure on diet and weight loss efforts, 87% of US adults are overweight or obese. Racial/ethnic disparities exist, with Non-Hispanic Black adults almost two times more likely than non-Hispanic Whites to have a T2D diagnosis (13.4% and 7.3% respectively). Blacks compared to Whites have a 50% higher morbidity and mortality and are at substantially higher risk of diabetes-related complications such as end stage renal disease and amputations. Evidence-based lifestyle interventions (LIs) to prevent T2D are available and demonstrate that weight loss as small as 5% is clinically meaningful, however 40-60% of intervention participants do not achieve the intervention weight loss goal. The original clinic-based Diabetes Prevention Program (DPP) LI clearly demonstrated that a LI that focused on a 7% weight reduction through changing behavior related to nutrition and increasing moderate intensity physical activity (PA) to 150 minutes weekly reduced incident diabetes by 58% among high-risk adults. The DPP used an intense one-on-one delivery model and included a "toolbox" of personalized strategies for use with individuals who were challenged with reaching the 7% weight loss goal. One on one approaches are not practical for public dissemination, thus upon translation and subsequent national dissemination of the DPP as the National DPP (NDPP), the paradigm has shifted among LIs to a group-based delivery model. Group based delivery is more cost effective than more resource intense one-on-one approaches, but with group-based delivery, all participants receive the same intervention regardless of their weight loss response. This "one size fits all" model is problematic because it does not account for heterogeneity in treatment response among participants. Previous research has translated the DPP to a variety of "real world" settings such as community centers, senior center and military bases to address issues of access and public health. Churches have been among these settings and the effectiveness of church-based health promotion interventions support previous research regarding the importance of providing contextual and culturally adapted interventions to racial/ethnic minority populations. This study seeks to establish the efficacy of identifying weight loss nonresponders early in a Diabetes Prevention Program (DPP) intervention in 20 community settings (primarily churches and community centers) and providing them with individual-level, enhanced treatment through telephone contacts and access to additional resources. We characterize nonresponse as a weight loss of less than or equal to 1% by week four of the intense phase of the intervention. Additionally, we will examine potential mediators and moderators of the relationship between intervention status and weight loss response at 6 months in both nonresponders and responders and lastly we conduct a cost effectiveness analysis to evaluate the cost of the intervention arm by comparing the incremental cost and weight loss with the active control arm. This study addresses key gaps in the literature about the weight loss effects of identifying nonresponders early and characterizing individuals who need more intense personalized strategies. We hypothesize that changes between baseline and 3 months will be more pronounced among the nonresponders in the intervention group compared to the nonresponders in the active control group.

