
## Objectives

List your research objectives. Please include a summary of intended research objectives in the box below.

The objectives of this pilot study are:

- 1) To evaluate differences over time in the primary outcome of weight, and secondary outcomes (i.e., PA level, blood pressure, and dietary behaviors) between nonresponders in the intervention group compared to nonresponders in the active control group.
- 2) To examine potential mediators and moderators of the relationship between intervention status and weight loss response at 6 months in both nonresponders and responders
- 3) Conduct a cost effectiveness analysis to evaluate the cost of the intervention arm by comparing the incremental cost and weight loss with the active control arm

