## Study Design

Describe and explain the study design (e.g., observational, secondary analysis, single/double blind, parallel, crossover, deception, etc.).

- **Clinical Research:** Indicate whether subjects will be randomized and whether subjects will receive any placebo.
- **Community-Based Participatory Research:** If you are conducting [community-based participatory research \(CBPR\)](#), describe strategies for involvement of community members in the design and implementation of the study, and dissemination of results from the study.
- **Qualitative research:** Indicate ranges where flexibility is needed, if a fixed interview transcript is not available, describe interview topics including the most sensitive potential questions.
- **Research Repositories:** If the purpose of this submission is to establish a Research Repository (bank, registry) and the material you plan to collect is already available from a commercial supplier, clinical lab, or established IRB approved research repository, provide scientific justification for establishing an additional repository collecting duplicate material. Describe the repository design and operating procedures. For relevant information to include, see the [UK Research Biospecimen Bank Guidance](#) or the [UK Research Registry Guidance](#).

This study is a two-group cluster randomized design to enroll and follow-up 500 participants over a period of 6 months.

Participants will be randomized by site assigned to:

- 1) DPP-GLB standard intervention (n=250)
- 2) DPP-GLB enhanced intervention (n=250)

We will involve our established Community Advisory Board through all stages of the intervention, from recommending community sites to engage in the project, to assisting with identifying Community Health Workers and reviewing project results prior to publication and presentations.

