## 2) DPP-GLB Enhanced Intervention Program (including telephone support)

### 2.a. Identification of Nonresponders:

At session four, the research data collector team member will weigh participants and calculate the percentage of weight loss. We will use percentage of weight loss rather than pounds because percentage is more applicable to a wide weight range and is consistent with the recommendations of the Obesity Society clinical guidelines. Participants who have lost less than or equal to 1% of their weight by 4 weeks will be defined as nonresponders and will remain nonresponders regardless of subsequent weight response. The nonresponders in both groups will continue with the standard DPP-GLB group-based intervention, however the nonresponders at the intervention sites will also receive the enhanced intervention delivered through weekly telephone support.

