### 2.b. Enhanced Intervention Calls:

The enhanced intervention will be delivered through weekly phone calls to the nonresponders. In addition to the nonresponders continued attendance at the DPP-GLB group sessions, beginning at week 5 the Community Health Worker will call each nonresponder weekly. During the brief call, the CHWs will use telephone scripts to guide the discussion with the nonresponder. Each script will begin with an open-ended question to assess the nonresponder's perspective of their progress and/or their weight loss barriers. The content of the script will align with the topic of the previous group session and guide the CHW in asking open-ended questions to elicit participant responses. We anticipate each call lasting ~15 minutes. During the call, the CHW will review the participant's self-monitoring log that each participant submits during the sessions and use motivational interviewing techniques to provide social support, assess the participants' barriers, resolve ambivalence regarding behavior change and to support the participant in developing their own strategies to overcome personal barriers. The content of the telephone script is under development and will be submitted to the IRB by amendment.

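### Week-4 loss defines Response status and precedes the calls, yet is an outcome level: valid nonresponder contrasts at weeks 12 and 24 remain available, but they should take account of week 4, and some other terms should not be interpreted

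*Combined protocol and SAP*

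**What the plan says.** The CT Gov analysis plan fits a repeated measures mixed model, allowing for the cluster design, to percent weight decrease at "timepoints of 4 weeks, 12 weeks, and 24 weeks, relative to weight at baseline". The factors are Time, Intervention Condition and Response status, and "we included the two- and three-way interaction terms".

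Two parts of Research Procedures fix the role of week 4. Section 2.a: "Participants who have lost less than or equal to 1% of their weight by 4 weeks will be defined as nonresponders". Section 2.b: "beginning at week 5 the Community Health Worker will call each nonresponder weekly". Until then both arms receive the same group sessions.

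The question to be answered is narrower than the model. Objective 1 is "To evaluate differences over time in the primary outcome of weight" and the secondary outcomes "between nonresponders in the intervention group compared to nonresponders in the active control group". The Background hypothesises that "changes between baseline and 3 months will be more pronounced among the nonresponders in the intervention group" than among control nonresponders. Study Design plans to "enroll and follow-up 500 participants over a period of 6 months".

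The analysis plan lists neither the cells nor the time points of its pre-planned comparisons. It chooses covariates by observed differences between arms or between completers and non-completers, and does not name week-4 loss among them.

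**The concern.** Week-4 loss appears on both sides of the model. Participants are split on it, and it is then one of the three outcome values compared between the groups so formed. A responder/nonresponder gap at week 4 is therefore certain, and it feeds the Response main effect and Response x Time whether or not early response predicts anything later.

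Week 4 also precedes the whole planned difference between the arms, so the expected arm effect there is zero. Averaging an arm effect over the three times mixes that zero with the two later effects.

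For the comparison that matters, nonresponders by arm, week-4 loss is a pre-call measure of the same outcome. A contrast at week 12 or 24 that ignores it usually gives away some precision. What is at stake is the interpretation of some model terms and the efficiency of the main contrast.

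**Working it through.** **Inputs.** From the documents: 20 sites, 10 per arm, 25 participants per site on target (500); the 1% cut at week 4; calls from week 5; outcome at weeks 4, 12 and 24. There is no stated power, SD, correlation, ICC or nonresponder share, so the plan has no figure to reproduce. Assumed: mean percent loss 1.5/3.5/4.0 and SD 1.8/4.0/5.5 at weeks 4/12/24; correlations 0.65 (4-12), 0.5 (4-24) and 0.8 (12-24); ICC 0.02; effect 1.5 points at weeks 12 and 24 in enhanced-site nonresponders.

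**1. Built-in Response gap.** For a normal week-4 loss cut at 1%, the gap is SD4 x phi(z)/[p(1-p)].
- z = (1 - 1.5)/1.8 = -0.278, so p = 0.391 and phi(z) = 0.384. The ratio is 0.384/(0.391 x 0.609) = 1.61.
- Week-4 gap: 1.8 x 1.61 = 2.90 points. Its share of the three-time average is 2.90/3 = 0.97, whatever the later correlation. Over SD4 of 1.2 to 2.4 it is 0.65 to 1.28.
- Later gaps from tracking: 0.65 x 4.0 x 1.61 = 4.19 and 0.5 x 5.5 x 1.61 = 4.43.
- Averaged gap: (2.90 + 4.19 + 4.43)/3 = 3.84. The week-4 level supplies 2.90/11.52 = 25%. The other 75% reflects the assumed tracking of later on early loss.

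**2. Averaging over time.** With arm effects 0, d12 and d24, the three-time mean is (0 + d12 + d24)/3 and the later mean is (d12 + d24)/2. The ratio is 2/3 for any d12 and d24 with a non-zero mean; this needs no assumed SD. In simulation, a true 1.5 is estimated as 0.98-1.00 over three times and 1.48-1.49 over weeks 12 and 24. Power barely moves (56% v 60%), because the standard error shrinks too.

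**3. What is unaffected.** Null rejection in simulation (site-level tests on 18 df, ICC 0.02 to 0.05) was 5.3% for Condition x Response, 4.8-5.8% for the three-way term, and 4.1-5.2% and 4.2-5.4% for the nonresponder contrast at weeks 12 and 24.

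**4. Taking account of week 4.** Within nonresponders the cut reduces the week-4 variance to a fraction 1 - z x l - l^2, with l = phi(z)/p = 0.983: 1 + 0.273 - 0.966 = 0.307. That gives 0.307 x 1.8^2 = 1.00. For week 4-12 correlation r, let b = r x 4.0/1.8. Ignoring clustering, the week-12 variance within nonresponders is:
- unadjusted: 16(1 - r^2) + b^2 x 1.00
- week-4 covariate: 16(1 - r^2)
- change from week 4: 16(1 - r^2) + (b - 1)^2 x 1.00

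| r | Unadjusted | Covariate | Change | Simulated power, unadjusted to covariate |
|---|---|---|---|---|
| 0 | 16.0 | 16.0 | 17.0 | 59 to 59% |
| 0.3 | 15.0 | 14.6 | 14.7 | 63 to 64% |
| 0.5 | 13.2 | 12.0 | 12.0 | 69 to 72% |
| 0.65 | 11.3 | 9.2 | 9.4 | 73 to 81% |
| 0.8 | 8.9 | 5.8 | 6.4 | 84 to 95% |

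At r = 0.65 a separate simulation gave 78 to 84%, and at ICC 0.05 the figures are 66 to 72%; the gain there is thus 6 to 8 points. Adjusted estimates were unbiased, with null rejection near 5%. Change from week 4 has power within about 2 points of the covariate analysis. At week 24 the gain is smaller: 41 to 45% at the base inputs.

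**5. Missing later weights.** With an assumed 18% missing them (about 25% of nonresponders, depending on week-4 loss and arm), change from week 4 and the covariate model without those participants both estimated 1.49 with 70% power. The week-12 contrast from the joint likelihood estimated 1.49 with 65%.

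**The case against.** The strongest reply is that the model already answers the question. Time, Condition and Response are fully crossed, so the nonresponder arm contrast at weeks 12 and 24 can be read from it without distortion. The Condition x Time contrast within nonresponders is the change from week 4, which fits the wording of Objective 1 on differences over time. This stands: the data layout is sound, and one of the two proposed analyses needs no new model.

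The plan also never says that it will report an arm effect averaged over the three times, or read a Response term as efficacy. This stands too. Those are cautions about terms that the model produces, not errors the plan commits.

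One could instead point to the extreme case. With zero correlation between week-4 and later loss, the Response main effect is significant in 88% of simulated trials with week 4 in the model, against 4-5% without it. That should not carry weight. The losses are cumulative from one baseline weight, so zero correlation is implausible, and under the base inputs three quarters of the averaged gap is tracking.

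Dropping week 4 as an outcome also has a cost: participants with no later weight leave the covariate model, whereas the plan keeps them in its analytic sample. They cost nothing in the one missingness pattern tried, but that pattern was assumed. What the reply does not remove is that the plan ties no contrast to the nonresponder hypothesis and does not say that the contrast will take account of week 4.

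**Conclusion.** The point holds as a cheap improvement that should be made. Two parts are independent of the assumed inputs: the week-4 level builds a gap into the Response main effect and Response x Time, and equal averaging over the three times scales an arm effect to 2/3 of its later mean when the week-4 arm effect is zero. The gain in week-12 power, 0 to about 11 points, depends on assumed SDs, correlations and ICC.

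A reader might infer that the primary nonresponder test is biased, or that a third of the power is lost. Neither follows. The contrasts at weeks 12 and 24 keep their error rate, and the 2/3 concerns an estimate that the plan does not commit to reporting.

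Both adjusted analyses assume that allocation did not affect week-4 loss. The common sessions support this, but sites are randomized before participants are recruited, and the Payment section gives a per-call incentive only to nonresponders at enhanced sites. That is a reason to check week 4 by arm. The documents give no evidence that anyone's weight was affected.

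**What to change.** - Answer Objective 1 and the Background hypothesis with the between-arm nonresponder contrast at week 12, and report week 24 as well.
- Take account of week-4 loss in one of two near-equivalent ways. (a) Use change from week 4 within the existing model, which keeps participants who miss both later weights. (b) Fit the 12- and 24-week outcomes in nonresponders, with week-4 loss as a continuous covariate, site as a random effect and repeated measures within participant.
- State that the Response main effect, Response x Time and any arm effect averaged over week 4 are not evidence of efficacy.
- Report week-4 loss and the share of nonresponders by arm.
- Label the result a revision and show it beside the original analysis, because the plan describes completed work.

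The cost is a few sentences of SAP text and one re-run. No new data are needed: Table 1 schedules weight at baseline, 4 weeks, 12 weeks and 6 months. The downsides are that (b) drops participants with no later weight, and (a) can lose a few points of power if the week-4 correlation is near zero (variance 17.0 v 16.0 above).
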